	 Incidence of perioperative serious adverse events (SAEs): Such as Mortality, Non-fatal myocardial infarction, Stroke, Cardiac perforation, Cardiac tamponade, etc. Allogeneic immune monitoring: PRA, DSA (2 week, 1, 3, 6 and 12 Month Post-operation) 					
	3. Perioperative cardiac monitoring: (1 Month Post-operation)					
	Efficacy:					
	Left ventricular function assessment:					
	2. Six-minute walk test: o Distance walked measured at 6 and 12 months postoperatively.					
	3. NYHA functional classification: • Assessed at 6, and 12 months postoperatively.					
	 4. Quality of life evaluation: Minnesota Living with Heart Failure Questionnaire (MLHFQ) administered at 6, and 12 months postoperatively. 					
	5. Major adverse cardiac events (MACE) incidence: o Mortality; Non-fatal myocardial infarction; Heart failure-related rehospitalization					
Statistical Methods and Data Analyses	The trial results will be analyzed primarily using descriptive statistics.					

	Continuous variables will be presented as mean ± standard deviation, along with median, minimum, and maximum values. 95% confidence intervals for means will be estimated using the t-distribution method. Between-group comparisons of means will be performed using Student's t-test. Categorical and ordinal data will be summarized as frequencies (percentages) and rates. 95% confidence intervals for rates will be calculated using the Miettinen method. Between-group comparisons of proportions will be conducted using Fisher's exact test. Longitudinal comparisons (e.g., PRA, DSA, 6-minute walk distance, NYHA functional class, MLHFQ scores) will be analyzed using repeated measures ANOVA to assess dynamic changes over time.
Duration	2 years

.

LIST OF ABBREVIATIONS

iPSC	Induced pluripotent stem cells
HF	Heart failure
CABG	Coronary artery bypass graft
ICD	Implantable cardioverter defibrillator
LVEF	Left ventricular ejection fraction
LVEDV	Left ventricular end-diastolic volume
LVESV	Left ventricular end-systolic volume
MRI	Magnetic resonance imaging
CT	Computed tomography
cTnI	Cardiac troponin I
cTnT	Cardiac troponin T
CKMB	Creatine phosphokinase-Mb
NT-proBNP	N-terminalpro-brain natriuretic peptide
PCT	Procalcitonin
TSH	Thyroid stimulating hormone
ECG	Electrocardiogram
NYHA	New York Heart Association
MACE	Major adverse cardiac events
MLHFQ	Minnesota Quality of Life Questionnaire for Heart Failure
6MWD	6min walking test distance
PCI	Percutaneous coronary intervention
HLA	Human leukocyte antigen

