2.2.2 Secondary endpoints

Efficacy:

- 1. Cardiac MRI Assessment of Left Ventricular Function:
 - o Comparative analysis of baseline versus postoperative measurements at 6, and 12 months, including: Infarcted size; End-diastolic lateral wall thickness; Focal septal thickness; Ejection fraction; End-diastolic volume; End-systolic volume; Stroke volume; Cardiac output; Myocardial density; End-diastolic myocardial mass
- 2. Echocardiographic Evaluation of Left Ventricular Function:
 - o Comparative analysis of baseline versus postoperative measurements at 6, and 12 months, including: End-diastolic septal thickness; Left ventricular end-diastolic

diameter; Left ventricular end-systolic diameter; Left ventricular posterior wall thickness at end-diastole; Left atrial diameter; Left ventricular ejection fraction; Mitral inflow velocity profile (E/A ratio)

- 3. Myocardial Perfusion Imaging (PET/ECT):
 - o Comparative analysis of left ventricular perfusion at preoperative, 6-month, and 12-month postoperatively
- 4. Six-Minute Walk Test (baseline, 6 and 12 months)
- 5. NYHA Functional Classification (baseline, 6 and 12 months)
- 6. Minnesota Living with Heart Failure Questionnaire (MLHFQ) (baseline, 6 and 12 months)
- 7. Incidence of Major Adverse Cardiac Events (MACE) including: Mortality; Non-fatal myocardial infarction; Heart failure rehospitalization

Safety:

- 1. Incidence of Perioperative Serious Adverse Events (SAE) Incidence: Mortality; Nonfatal myocardial infarction; stroke; cardiac perforation; cardiac temponade, etc.
- 2. Alloimmune Response Monitoring (PRA, DSA): (baseline, 1, 6 and 12 months)
- 3. Perioperative Electrocardiographic Monitoring (Within 1 month postoperatively)
- 4. Laboratory Tests, including Complete blood count, Comprehensive metabolic panel; NT-proBNP;Troponin; Myocardial enzyme profile; Procalcitonin; Immunological panel (C3, C4, IgA, IgG, IgM); Coagulation profile, etc.

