6.3 Sample Size Determination

This is an exploratory study. The total sample size is 20, with 10 allocated to the cell therapy group and 10 to the control group

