6.5.2 Secondary endpoint analysis

Secondary endpoints were analyzed using descriptive statistics. The comparative assessment of treatment effects employed distinct analytical approaches based on variable characteristics. Continuous variables are presented with mean, standard deviation, median, maximum and minimum values, and range, compared using the t-test method. Categorical and ordinal data are reported as frequencies (percentages), compared using the Wilcoxon rank-sum test. A two-sided p-value of ≤ 0.05 was considered statistically significant for all analyses.

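### Section 6.5.2 labels every unadjusted secondary result with p ≤ 0.05 statistically significant, in an exploratory trial that names no lead efficacy measure, modality or visit

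*Protocol*

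**What the plan says.** Section 6.5.2 of the protocol opens by saying that secondary endpoints are analysed descriptively. It then prescribes comparative tests: continuous variables are "compared using the t-test method", and categorical and ordinal data are "compared using the Wilcoxon rank-sum test". It ends with the rule at issue, that a two-sided p-value of 0.05 or less "was considered statistically significant for all analyses".

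Other parts of the protocol set a different tone. Section 6.3 says "This is an exploratory study" and gives no power calculation. The synopsis, under statistical methods, says "The trial results will be analyzed primarily using descriptive statistics". Section 2.2.1 makes both primary endpoints safety endpoints (sustained ventricular tachycardia and new tumours), while the objective in section 2.1 covers efficacy as well as safety.

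Section 2.2.2 holds the efficacy measures. The cardiac MRI list begins "Infarcted size; End-diastolic lateral wall thickness; Focal septal thickness; Ejection fraction" and runs to ten parameters. Echocardiography adds seven, including ejection fraction a second time. Perfusion imaging, the six-minute walk, NYHA class and the MLHFQ follow. All are assessed at 6 and 12 months. No measure, modality or visit is given precedence, and the protocol nowhere says that secondary p-values are nominal.

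**The concern.** An exploratory trial of 20 patients need not control the error rate across its secondary endpoints, and this point does not ask for that. The difficulty is narrower. The protocol itself attaches the label of statistical significance to any secondary comparison that crosses 0.05, without adjustment and without ranking.

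Since no primary endpoint measures efficacy, every efficacy statement must come from this unranked list. A report could lead with whichever ejection fraction modality or visit crossed 0.05 and still comply with the protocol. A reader of that report could not tell a prespecified main result from the most favourable of many.

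**Working it through.** The protocol states no number of tests, overall error rate or power, so there is no figure of its own to reproduce. The steps below rebuild the number of comparisons and what the rule yields if the cells have no effect.

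**Inputs from the protocol**
- Threshold per test: 0.05, two-sided (6.5.2).
- Serial efficacy measures (2.2.2): 10 MRI + 7 echocardiography + 1 perfusion + six-minute walk + NYHA + MLHFQ = 21. Perfusion is counted once.
- Post-baseline visits: 2 (6 and 12 months).
- Patients: 10 per arm (6.3).

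**Assumptions, since the protocol is silent**
- Tests per measure: one per visit, or one in all.
- Correlation between the test outcomes: a common value, varied from 0 to 0.9.

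**Step 1: number of tests**
- One between-group test per measure and visit: 21 × 2 = 42.
- The synopsis's repeated measures ANOVA replaces the visit-wise tests for six-minute walk, NYHA and MLHFQ: 42 − 3 = 39.
- That ANOVA covers every serial measure, with one group-level test each: 21.

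**Step 2: expected number of results labelled significant under no effect**

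The expected number is the number of tests × 0.05, and it does not depend on correlation.
- 42 × 0.05 = 2.1
- 21 × 0.05 = 1.05

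**Step 3: chance of at least one, if the tests were independent**

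The formula is 1 − 0.95^k.
- k = 42: 88.4%
- k = 39: 86.5%
- k = 21: 65.9%

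These are upper-end values. Stroke volume is the difference of the two ventricular volumes, ejection fraction is derived from them, cardiac output follows from stroke volume, and each measure is repeated in the same patients. Independence therefore cannot hold.

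**Step 4: chance of at least one, with correlation**

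This was simulated with 20,000 trials per setting, 10 per arm, normal outcomes and a two-sided t-test for every measure. The t-test only approximates the rank test prescribed for NYHA.

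| Common correlation | 42 tests | 21 tests |
|---|---|---|
| 0.3 | 77% | 56% |
| 0.5 | 61% | 45% |
| 0.6 | 50% | 38% |
| 0.7 | 40% | 32% |
| 0.8 | 29% | 24% |
| 0.9 | 20% | 17% |

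A structured version with 42 tests, using correlation 0.3 between measures and 0.7 between visits, gives 76%.

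**Step 5: ejection fraction alone**

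Two modalities × two visits = 4 tests. Independence gives 1 − 0.95^4 = 18.5%. Simulation with correlations of 0.7 to 0.8 gives about 13–14%, against 5% for a single named test.

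**Step 6: is full correction an alternative?**

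Bonferroni over 42 tests sets 0.05/42 = 0.00119 per test. With 10 per arm, 80% power then needs a difference of 2.14 SD, against 1.32 SD at 0.05. Full correction is not practical in this trial.

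**The case against.** The strongest reply is that nothing depends on these p-values. The protocol has no efficacy success criterion, no power claim and no efficacy hypothesis, and it calls itself exploratory and descriptive. A threshold of 0.05 is then an ordinary per-comparison convention that holds 5% for each test, and any misuse would lie in the reporting. Ranking of secondary endpoints is also commonly left to a statistical analysis plan, which may exist.

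Much of this stands. A reader might infer that 6.5.2 sets up a confirmatory test of efficacy; the documents do not support that, because no trial conclusion is tied to a secondary p-value. The figure of 42 is a reconstruction. The synopsis names repeated measures ANOVA for longitudinal comparisons with only examples of the variables, so 21 is an admissible reading.

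A reader might also infer that a false positive is likely in any case. With 42 tests that holds only up to a common correlation of about 0.6. With 21 tests the chance is already below one half at 0.5. Nor should the count be enlarged with MACE and laboratory results, because section 6.5.3 only counts or summarises those and names no test.

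The reply does not remove the rule itself. The significance label is written into the protocol for all analyses and is not a detail left open. It also conflicts with the descriptive purpose stated in the synopsis and at the start of the same section.

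**Conclusion.** The point holds as a defect in a stated rule. Followed as written, 6.5.2 would on average label about 2 of 42 null comparisons, or about 1 of 21, as statistically significant. That expectation depends only on the number of tests.

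The chance of at least one such result does depend on correlation, for which the documents give no figure. With 42 tests it runs from 88% under an unrealistic independence to about 20% at 0.9, which is still four times the nominal 5%. For ejection fraction alone it is about 13–14% at correlations of 0.7 to 0.8.

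The descriptive analysis of the two primary safety endpoints is unaffected. What is exposed is the credibility of any efficacy statement. The protocol should be changed, but the matter is one of labelling and ranking and does not call for alpha adjustment.

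**What to change.** Replace the last sentence of 6.5.2 with: *Secondary p-values are nominal and descriptive; no claim of statistical significance rests on them; between-group differences are reported with 95% confidence intervals.*

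Add a second sentence, fixed before analysis, that names one lead efficacy measure with its modality and visit and labels all other efficacy measures supportive. Baseline-adjusted ejection fraction by MRI at 12 months would be one example; the choice is the sponsor's. Section 6.4 already provides blinded assessors for efficacy.

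The synopsis already plans 95% intervals for means and rates, so intervals for differences are a small extension. The change needs no further patients, visits or data. What is given up is the word significant for unadjusted secondary results.

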6.5.3 Safety Analyses

Adverse events will be described using the preferred terms from the MedDRA terminology. All adverse events will be graded for severity according to the Common Terminology Criteria for Adverse Events (CTCAE), version 5.0. For Major Adverse Cardiac Events (MACE), including arrhythmias, and for other adverse events and adverse drug reactions distinct from arrhythmias, the number of events and the number of subjects experiencing these events will be determined. Adverse events assessed as Serious Adverse Events (SAEs) will be identified, and the number of such SAEs and the number of subjects experiencing SAEs will be determined. For significant events related to Coronary Artery Bypass Graft (CABG), the number of events and the number of subjects experiencing these events will be determined. Adverse events occurring during or within a specified period following the first administration of the investigational medicinal product will be summarized by CTCAE grade.

Clinical laboratory parameters, vital signs, and physical examination findings will be summarized according to study visit. The analysis will describe the observed values at each visit during the trial as well as the changes relative to baseline values.

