2.2 Study Endpoints

2.2.1 Primary endpoints

Safety:

- 1. Incidence of sustained ventricular tachycardia (1~6 Month Post-operation)
 - o Defined as the proportion of patients experiencing ventricular tachycardia lasting more than 30 seconds
- 2. Incidence of newly formed tumors (12 Month Post-operation)
 - o By comparing chest, abdominal and pelvic CT scan and PET-CT scan

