4 STUDY TREATMENT

4.1 Treatment and dosage

4.1.1 Treamtment

All enrolled subjects will undergo standardized coronary artery bypass grafting (CABG) in accordance with established clinical guidelines. For patients in the cell therapy group, the treatment protocol incorporates myocardial cell transplantation alongside the standard CABG procedure. Following completion of graft anastomoses, a total of 2×10^8 allogeneic human regenerative cardiomyocytes are administered via epicardial injection at 10 sites surrounding the infarcted myocardial region.

Patients in the Cell therapy group were administered the following immunosuppressive regimen: intravenous immunoglobulin (2.5 g, IV) on preoperative day 1, intraoperative day (IOD), and postoperative day (POD) 3, combined with methylprednisolone (500 mg, IV) on preoperative day 1; rituximab (20 mg, IV) on IOD and POD4 to target CD20+ B-cell depletion; oral tacrolimus started preoperative day 3 and dose-adjusted to maintain trough levels within the target range of 3-5 ng/mL, as monitored by blood drug concentration until POD28, concurrently with mycophenolate mofetil (1 g, orally on preoperative day 1, increasing to 1.5 g/day until POD28) and prednisone (20 mg/day started IOD until POD28). The Control group did not receive any immunosuppressive medications. All study subjects

Protocol (version 6.1)

Version data: 2021.08.01

Confidential
Page 19 of 38

undergo intensive postoperative monitoring in the ICU with comprehensive emergency protocols implemented as needed.

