4.1.2 Dosage form and dosage

Cell Type: Allogeneic human regenerative cardiomyocytes

[figure not shown]
Dosage: A total of 2×10^8 cells are administered via intramyocardial injection, divided equally across 10 sites (250–500 µL per injection).

Administration: The procedure is performed intraoperatively following completion of graft anastomoses during CABG.

Control Group receive standardized CABG alone.

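### Section 6.5.3 adds arrhythmias to MACE against the endpoint definition and gives controls no start for the CTCAE-grade summary, and Table 3 begins adverse-event recording after cell-arm drugs have started

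*Protocol*

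**What the plan says.** **MACE.** Section 2.2.2 lists, under efficacy, "Incidence of Major Adverse Cardiac Events (MACE) including: Mortality; Non-fatal myocardial infarction; Heart failure rehospitalization". The synopsis gives the same three components, also under efficacy. Section 6.5.3 describes its tabulation as "For Major Adverse Cardiac Events (MACE), including arrhythmias, and for other adverse events and adverse drug reactions distinct from arrhythmias", and for these groups "the number of events and the number of subjects experiencing these events will be determined".

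**Summary by grade.** Section 6.5.3 grades all adverse events by CTCAE version 5.0, but the summary by grade is restricted: "Adverse events occurring during or within a specified period following the first administration of the investigational medicinal product will be summarized by CTCAE grade". Section 4.1.2 states: "Control Group receive standardized CABG alone". Section 4.1.1 adds that controls have no immunosuppression.

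**Recording of adverse events.** The adverse-event row of Table 3 is blank in the baseline column (D-14 to D-1) and marked from D0 to month 12, with no split by arm. In the cell arm, section 4.1.1 has "oral tacrolimus started preoperative day 3", with immunoglobulin, methylprednisolone and mycophenolate mofetil on preoperative day 1. Section 8.3 promises close safety monitoring for as long as these drugs are given.

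**Allocation.** Section 6.4 has the envelope opened immediately before surgery.

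**The concern.** MACE is a listed secondary endpoint. Section 6.5.2 compares categorical secondary endpoints between arms at a two-sided 0.05 level. If two sections define the composite differently, the reported rate depends on which section the analyst follows, and that choice could be made after the data are seen. Arrhythmia is also looked for intensively here: Holter recording at six postoperative points in Table 3, plus continuous ECG monitoring around the procedure and remote monitoring after discharge in section 8.4. An unqualified arrhythmia component could therefore outweigh the other three.

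The summary by grade is the only table in section 6.5.3 laid out by severity. Without a start date for controls, it cannot set the arms side by side.

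Section 8 names adverse effects of the immunosuppressive drugs as one of the primary risks. A schedule that begins recording after those drugs begin does not cover the first days of that risk.

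**Working it through.** The protocol states no event rate, power or effect size for MACE or adverse events, so there is no figure to reproduce. The check is mainly a comparison of sections.

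**1. MACE components**

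| Place | Death | Non-fatal MI | HF rehospitalisation | Arrhythmia |
|---|---|---|---|---|
| Synopsis | yes | yes | yes | no |
| Section 2.2.2 | yes | yes | yes | no |
| Section 6.5.3 | not listed | not listed | not listed | yes, no type, duration or grade |

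The second half of the 6.5.3 sentence sets the remaining events apart from arrhythmias, so it places arrhythmia in the MACE group. Sustained ventricular tachycardia in months 1 to 6 would count both as a primary endpoint and as MACE.

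**2. Whether the definition could matter at this size.** The counts here are assumptions. The test is two-sided Fisher, as named in the synopsis for proportions, with 10 patients per arm.

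- Three-component MACE in 1/10 v 1/10: p = 1.00.
- Add patients with arrhythmia only, in the cell arm, to reach 3, 4, 5, 6 or 7 of 10 v 1/10: p = 0.58, 0.30, 0.14, 0.057, 0.020.
- Add such patients in both arms: 6/10 v 3/10 gives p = 0.37, and 7/10 v 3/10 gives p = 0.18.

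For 7/10 v 1/10: p = 2 × [C(10,7)·C(10,1) + C(10,8)·C(10,0)] / C(20,8) = 2 × (1200 + 45) / 125970 = 0.020.

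The definition can change the result, but on these counts it crosses 0.05 only when six more patients in the cell arm, and none in the control arm, have arrhythmia alone.

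**3. Starting point of each safety count in 6.5.3**

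- MACE, other adverse events and adverse drug reactions: not tied to the product.
- Serious adverse events: not tied to the product.
- CABG-related events: not tied to the product.
- Summary by CTCAE grade: tied to first administration of the product.

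Allocation is 10 + 10 = 20 (section 6.3). Controls with a qualifying start date for the grade summary: 0 of 10. In the cell arm the cells are injected after the graft anastomoses are complete. If the product means the cells, that arm's clock starts during the operation, after the preoperative drugs.

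**4. Recording before surgery.** Table 3 has eight time columns. The adverse-event row has seven marks, and the blank is baseline. With tacrolimus from preoperative day 3, the days D-3, D-2 and D-1 are days of cell-arm drug exposure with no adverse-event mark.

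**5. Whether allocation could be the start.** Section 6.4 puts the opening of the envelope immediately before surgery, in effect D0. Recording from allocation would recover none of those three days. The same comparison shows a further contradiction: drugs given only to the cell arm start before the arm is revealed.

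**The case against.** **The safety comparison as a whole fails.** A reader might infer this, and the documents do not support it. The product anchor governs one sentence. The counts of adverse events, drug reactions, serious events and CABG-related events carry no such anchor, Table 3 gives both arms a common D0, and section 3 gives both arms identical follow-up. All 20 patients stay in those counts. Section 6.5.3 itself is descriptive and names no test between arms.

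**MACE has no usable definition.** Nor does this follow. Both places that define endpoints agree on three components and list MACE under efficacy. The phrase in 6.5.3 could be a loosely worded tabulation group, and overlap between a composite and a primary endpoint is not in itself an error. What stands is that 6.5.3 contradicts the endpoint lists. The word introducing the list in 2.2.2 could be read as open-ended, but the synopsis gives the same three items as a plain list.

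**The analysis plan may settle it.** The length of the window after administration may well be set there, and its absence here is not a fault. A window length does not help controls, however, because they have no administration to count from. A different reference point is needed.

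**Preoperative reactions are lost altogether.** This is also too strong. Section 8.3 promises monitoring throughout dosing, and section 9.1 makes the sponsor responsible for seeing that all adverse events and reactions are reported. The defect is that the schedule does not match that text, so capture before D0 is left to chance.

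**The inflation of MACE can be quantified.** Only by assuming arrhythmia rates that the protocol does not give.

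**Conclusion.** The point holds in three limited parts. First, 6.5.3 contradicts the synopsis and 2.2.2 on what counts as MACE. Second, the CTCAE-grade summary, and only that summary, has no start for 10 of 20 patients if read literally. Third, Table 3 schedules no adverse-event recording on three preoperative days when cell-arm patients already receive immunosuppression, against the monitoring that section 8.3 promises.

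The effect on the MACE result cannot be sized from the protocol. The Fisher figures are illustrations on assumed counts and show only that the choice of definition could matter. The 10 of 20 rests on taking first administration literally. The three days rest on preoperative day 3 meaning D-3.

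These rules would mislead if followed as written and should be corrected. They do not invalidate the three-component MACE endpoint or the adverse-event counts that are not tied to the product.

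**What to change.** 1. In 6.5.3, remove arrhythmias from MACE so that it matches the synopsis and 2.2.2, and report arrhythmias as their own category.
2. Anchor the CTCAE-grade summary to the day of surgery (D0), with the same window in both arms.
3. Start adverse-event recording in both arms at a common point before the first preoperative study drug, such as consent or the baseline window. Mark this in Table 3 and tabulate events before D0 separately. Do not use allocation as the start.
4. Reconcile sections 4.1.1 and 6.4 on the order of the cell-arm preoperative drugs and the opening of the envelope. Which of the two should change is for the sponsor and the investigator to decide.

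Items 1 and 2 are wording changes. Item 3 changes the adverse-event row of Table 3 and adds a short table. The downside is slightly more events recorded, including some before surgery that are unrelated to treatment.

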8.4 Post-Transplant Ventricular Arrhythmias Risks and Control

Fatal malignant ventricular arrhythmias constitute a potentially severe risk associated with myocardial cell therapy. Ventricular arrhythmias, particularly polymorphic ventricular tachycardia and ventricular fibrillation, represent significant in-hospital causes of early mortality in myocardial infarction (MI) patients. The resulting tissue architecture, comprising necrotic scar, border zones, and viable myocardium, creates regions of heterogeneous electrophysiology, particularly within the peri-infarct zone, fostering anisotropic conduction and reentrant circuits. Cell therapy targeting the infarcted myocardium inherently modifies this arrhythmogenic substrate. Theoretically, such interventions carry dual potential: therapeutic augmentation of the substrate may reduce arrhythmia susceptibility, while proarrhythmic exacerbation remains a concurrent possibility. Whether cell therapy exerts proarrhythmic effects depends critically upon multiple factors: (1) the specific cell type employed; (2) the degree of electrophysiological integration and coupling between transplanted cells and native myocardium; and (3) intrinsic electrophysiological properties of the transplanted cells themselves. Transplanted cells may introduce novel proarrhythmic substrates by establishing reentrant pathways within scar tissue or inducing arrhythmias via mechanisms of ectopic automaticity or triggered activity.

Animal experimental evidence regarding the proarrhythmic effects of cell-based therapies remains limited and conflicting. Some studies indicate that transplanted cells, which originally lack connexin 43 expression, can acquire this critical gap junction protein postengraftment; connexin 43 is essential for facilitating coordinated electrical conduction within myocardial tissue. However, persistent concerns exist based on studies suggesting that cardiomyocytes derived from embryonic stem cells (ESCs) may harbor intrinsic proarrhythmic risks. Notably, research by Shiba et al. demonstrated that treatment of heart failure in nonhuman primates using induced pluripotent stem cell (iPSC)-derived cardiomyocytes did not result in fatal arrhythmias [18].

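### MACE has three components in the synopsis and section 2.2.2 but also takes in arrhythmias in section 6.5.3, whose wording leaves product-related arrhythmias no stated place in the adverse-reaction count

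*Protocol*

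**What the plan says.** Section 2.2.2 of the protocol lists as efficacy item 7: "Incidence of Major Adverse Cardiac Events (MACE) including: Mortality; Non-fatal myocardial infarction; Heart failure rehospitalization". The synopsis gives the same three components under its efficacy item 5: "Mortality; Non-fatal myocardial infarction; Heart failure-related rehospitalization". Neither place names arrhythmia.

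Section 6.5.3 (Safety Analyses) is the only analysis text that names MACE. It begins: "For Major Adverse Cardiac Events (MACE), including arrhythmias, and for other adverse events and adverse drug reactions distinct from arrhythmias", and continues that "the number of events and the number of subjects experiencing these events will be determined".

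Other sentences of 6.5.3 are general and exclude nothing:
- adverse events are summarised by MedDRA preferred term
- on severity, "All adverse events will be graded for severity according to the Common Terminology Criteria for Adverse Events (CTCAE), version 5.0"
- for SAEs, "the number of such SAEs and the number of subjects experiencing SAEs will be determined"

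Section 8.4 says of the risk itself: "Fatal malignant ventricular arrhythmias constitute a potentially severe risk associated with myocardial cell therapy". The opening of section 8 lists ventricular arrhythmia as one of three primary risks. Sustained ventricular tachycardia in months 1 to 6 is one of the two primary endpoints in section 2.2.1.

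**The concern.** There are two problems in one sentence.

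First, the MACE label covers two event sets. Under 6.5.3 as worded, any arrhythmia counts as a major cardiac event, however brief or mild. The trial looks hard for arrhythmias: Table 3 schedules Holter recordings in D1-D7, at D14 and D21, and at months 1, 6 and 12, and section 8.4 adds continuous peri-procedural ECG and remote monitoring after discharge. The two event sets could therefore give quite different rates. A later analysis plan cannot follow both passages. Unless the protocol settles the matter, which rate carries the name MACE could be decided after arrhythmias by arm are known in an open-label trial.

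Second, the sentence counts adverse drug reactions only where they are distinct from arrhythmias. A reader looking in the reaction count for a foreseen product-related harm would not find it there.

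**Working it through.** **MACE definition, side by side**

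| Place | Death | Non-fatal MI | HF rehospitalisation | Arrhythmia |
|---|---|---|---|---|
| Synopsis, efficacy item 5 | yes | yes | yes | not listed |
| Section 2.2.2, efficacy item 7 | yes | yes | yes | not listed |
| Section 6.5.3 | components not restated | components not restated | components not restated | included, no limit on type, duration or grade |

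**Size of the gap.** The protocol states no MACE rate, arrhythmia rate or power, so there is no figure to reproduce. What follows is illustration.

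- *Step per patient.* Section 6.3 allocates 10 patients to each arm. One patient with an arrhythmia and none of the three components moves the arm's rate by 1/10 = 10 percentage points.
- *Assumed rates.* Let m be the three-component MACE rate and a the proportion with any arrhythmia, taken as independent. The broad rate is 1 − (1 − m)(1 − a).

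| m | a = 10% | a = 20% | a = 30% | a = 40% |
|---|---|---|---|---|
| 10% | 1 − 0.9×0.9 = 19% | 1 − 0.9×0.8 = 28% | 1 − 0.9×0.7 = 37% | 1 − 0.9×0.6 = 46% |
| 20% | 1 − 0.8×0.9 = 28% | 1 − 0.8×0.8 = 36% | 1 − 0.8×0.7 = 44% | 1 − 0.8×0.6 = 52% |

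- *Precision.* If three patients in an arm are reclassified, 1/10 = 10% (exact 95% limits 0.3% to 44.5%) becomes 4/10 = 40% (12.2% to 73.8%).
- *Between-arm comparison, extreme case.* Suppose each arm has 1/10 by the three-component definition (Fisher p = 1.0), and five further patients, all in the cell arm, have an arrhythmia. The comparison becomes 6/10 against 1/10. Two-sided Fisher p = 2 × (2100 + 120)/77520 = 0.057. With six further patients (7/10 against 1/10), p = 0.020.

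**Where an arrhythmia is counted under 6.5.3**

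| Count or summary | Is arrhythmia in it? |
|---|---|
| MACE line | yes, events and subjects |
| MedDRA preferred terms | yes, not excluded |
| CTCAE grading and summary by grade | yes, not excluded |
| SAE count | yes, if serious |
| Other adverse events, same sentence as MACE | no, by its wording |
| Adverse drug reactions, same sentence as MACE | no, by its wording |

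The last row matters because no other sentence in section 6.5 counts adverse drug reactions. The remaining summaries sort by term, grade or seriousness, not by relation to the product. The primary endpoint does not fill the gap. It covers ventricular tachycardia longer than 30 seconds in months 1 to 6, so it leaves out ventricular fibrillation, non-sustained arrhythmia and, if the window is read as starting at month 1, events in the first month.

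**The case against.** The strongest reply is that 6.5.3 is a safety section. It nowhere says that its MACE count replaces the efficacy endpoint of 2.2.2, which as a secondary endpoint falls under 6.5.2. The reference to events distinct from arrhythmias can be read as avoiding a double count within one sentence. The trial is exploratory, has 20 patients and is mainly descriptive, and MACE is the last of seven efficacy items. All of this is fair. It lowers the severity, but one label still has two scopes.

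It can also be said that 2.2.2 introduces its components with a word that need not close the list. That is so, but the synopsis gives the same three as a plain list.

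A reader might infer more than the protocol supports:

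- *That arrhythmias drop out of adverse-event reporting.* They do not. The MedDRA, CTCAE and SAE sentences keep them, the MACE line counts them, and sustained ventricular tachycardia is a primary endpoint. Only the reaction count lacks a stated place for them, and only on a literal reading.
- *That arrhythmia is the main harm expected from the cells.* Section 8 lists it third of three primary risks, without ranking. Section 8.4 allows that susceptibility may fall as well as rise and calls the product's proarrhythmic potential theoretical.
- *That the definition decides which arm looks better.* The two-arm example puts every extra arrhythmia in the cell arm and none among ten control patients who also have surgery. With five extra patients it still misses the 0.05 level of section 6.5.2, and it takes six to cross it. The example shows what is possible, not what is likely.

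**Conclusion.** The point holds in a limited form and should be fixed. The inconsistency in the MACE definition rests on the text alone. Its size does not: the 10-point step per patient follows from the sample size, but the range of 19% to 46% depends on an assumed 10% three-component rate, assumed arrhythmia rates of 10% to 40%, and independence between them.

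The gap in the adverse-reaction count rests on a literal reading of one sentence. It concerns where related arrhythmias are tabulated, not whether they are reported. The protocol does not support a claim that the cell arm's reaction rate will be understated as a matter of fact. The primary endpoints, the sample size and the randomisation are unaffected.

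**What to change.** Revise the one sentence in section 6.5.3:

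1. Delete 'including arrhythmias', and refer to the three-component MACE of section 2.2.2 wherever the term is used.
2. Report arrhythmias as a category of their own, by events and by subjects.
3. Delete 'distinct from arrhythmias', so that an arrhythmia judged to be an adverse event or an adverse drug reaction is counted there too.
4. Say that one arrhythmia may then appear in more than one table, so the categories are not to be added together.

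How arrhythmias are subdivided can be left to the analysis plan. The cost is a wording change to one sentence, with no new data, visits or assessments. It should be made before any comparison by arm is seen.
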